### 3.2.6 Regulatory Requirements

#### 3.2.6.1 Each patient's parents or legal guardians must sign a written informed consent.

#### 3.2.6.2 All institutional, FDA, and NCI requirements for human subjects research must be met.

## 3.3 **Definitions**

### 3.3.1 Transient myeloproliferative disease (TMD)

A disorder of fetal hematopoiesis defined by the presence of circulating non-lymphoid, non-erythroid blasts in the blood of infants (< 90 days of age) with constitutional trisomy 21 or trisomy 21 mosaicism.

Note: the resolution date of TMD is defined as the date when blasts, abnormal blood counts and clinical signs of TMD were first documented as resolved.

### 3.3.2 CNS Leukemia

#### 3.3.2.1 CNS disease at diagnosis is defined as:

- Any number of blasts on a cytopspin prep in an atraumatic (< 100 RBCs) lumbar puncture.
- Blasts in a traumatic tap in which the WBC/RBC ratio in the CSF is twice that in the peripheral blood.
- Clinical signs of CNS leukemia (such as facial nerve palsy, brain/eye involvement or hypothalamic syndrome). Extra-ocular orbital masses are not considered CNS leukemia.
- Radiographic evidence of an intracranial, intradural mass consistent with a chloroma.

See [Appendix V](#) for more details.

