#### 3.3.2.2 Method of Evaluating Initial Traumatic Lumbar Punctures:

If the patient has leukemic cells in the peripheral blood and the lumbar puncture is traumatic and contains blasts, the following algorithm should be used to diagnose CNS disease:

$$\frac{\text{CSF WBC}}{\text{CSF RBC}} > 2X \quad \frac{\text{Blood WBC}}{\text{Blood RBC}}$$

A patient with CSF blasts, whose CSF WBC/RBC is 2X greater than the blood WBC/RBC ratio, has CNS disease at diagnosis. For example: CSF WBC = 60/ $\mu$ L; CSF RBC = 1,500/ $\mu$ L; blood WBC = 46,000/ $\mu$ L; blood RBC = 3  $\times$  10^6/ $\mu$ L:

$$\frac{60}{1,500} = 0.04 \quad > 2X \quad \frac{46,000}{3 \times 10^6} = 0.015$$

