##### **Intrathecal Cytarabine:**

The dose of intrathecal (IT) cytarabine may be given at the time of the diagnostic lumbar puncture. If IT cytarabine is not given at time of diagnostic LP, then administer on Day 1 of Induction I. If IT cytarabine is given prior to diagnosis, a separate institutional consent must be obtained.

Age-based dosing:

Age (months):	Dose:
0 to < 13 months	20 mg
13 to < 25 months	30 mg
25 to < 36 months	50 mg
≥ 36 to < 48 months	70 mg

**For CNS positive patients:** IT cytarabine will be given twice weekly until the CSF is clear plus two additional intrathecal treatments (for a minimum of 4 and maximum of 6 doses). Patients with persistent CNS leukemia after 6 doses of IT cytarabine will be taken off protocol therapy.

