## APPENDIX V: DEFINITION OF CNS LEUKEMIA

- CNS 1: In cerebral spinal fluid (CSF), absence of blasts on cytopsin preparation, regardless of the number of white blood cells (WBCs).
- CNS 2a:  $< 10/\mu\text{L}$  RBCs;  $< 5/\mu\text{L}$  WBCs and cytopsin positive for blasts.
- CNS 2b:  $\geq 10/\mu\text{L}$  RBCs;  $< 5/\mu\text{L}$  WBCs and cytopsin positive for blasts.
- CNS 2c:  $\geq 10/\mu\text{L}$  RBCs;  $\geq 5/\mu\text{L}$  WBCs and cytopsin positive for blasts but negative by Steinherz/Bleyer algorithm.
- CNS 3a:  $< 10/\mu\text{L}$  RBCs;  $\geq 5/\mu\text{L}$  WBCs and cytopsin positive for blasts.
- CNS 3b:  $\geq 10/\mu\text{L}$  RBCs,  $\geq 5/\mu\text{L}$  WBCs and cytopsin positive by Steinherz/Bleyer algorithm.
- CNS 3c: Clinical signs of CNS leukemia (such as facial nerve palsy, brain/eye involvement or hypothalamic syndrome).

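### Section 3.3.2 and Appendix V classify blast-positive lumbar punctures differently, the trigger for extra intrathecal cytarabine is tied to neither, and CSF clearance at dose 5 or 6 is not covered

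*Combined protocol and SAP*

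**What the plan says.** Section 3.3.2.1 lists what counts as CNS disease at diagnosis. The first criterion is "Any number of blasts on a cytopspin prep in an atraumatic" tap, where atraumatic means fewer than 100 RBCs. No unit is given for the 100. The second is "Blasts in a traumatic tap in which the WBC/RBC ratio in the CSF is twice that in the peripheral blood". Section 3.3.2.2 confines the ratio test to the second situation: if "the lumbar puncture is traumatic and contains blasts, the following algorithm should be used to diagnose CNS disease". Section 3.3.2.1 then refers the reader to Appendix V "for more details".

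The appendix is headed "APPENDIX V: DEFINITION OF CNS LEUKEMIA". It sorts taps into CNS 1, 2a–c and 3a–c. Its RBC division is at 10/µL, and its WBC division is at 5/µL. The algorithm enters only when RBCs are at least 10/µL and WBCs at least 5/µL: a positive result is 3b, and 2c is the class with "WBCs and cytopsin positive for blasts but negative by Steinherz/Bleyer algorithm". It does not say which grades count as CNS positive.

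The Induction I delivery map (Section 4.2.1) and Section 4.2.3 give additional intrathecal cytarabine to CNS-positive patients. Doses are twice weekly until the CSF is "clear plus two additional intrathecal treatments (for a minimum of 4 and maximum of 6 doses"). Section 4.2.3 and Section 8.1(b) take a patient off protocol therapy if CNS leukemia persists after 6 doses.

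**The concern.** There are two separate problems.

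1. **Who is CNS positive.** The main text and the appendix it cites use different RBC limits and apply the ratio to different taps. The dosing sections use a third term, CNS positive, and define it by neither scheme. Two sites with the same tap could therefore treat the child differently in good faith. Section 4.1.5 gives high-risk patients no intrathecal therapy after Induction I, so a difference here is not made up later on protocol. It also decides who can reach the six doses on which removal under Section 8.1(b) depends.

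2. **Late clearance.** Two doses after clearance and a ceiling of six cannot both be met if the CSF first clears near the ceiling. Such a child no longer has persistent disease, so the removal rule does not cover the case either.

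**Working it through.** **Inputs**

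- Section 3.3.2.1: below 100 RBCs, any blasts are CNS disease. I read the 100 as per µL; this is an assumption, because no unit is stated.
- Section 3.3.2.2: a traumatic tap with blasts is CNS disease if CSF WBC/RBC > 2 × blood WBC/RBC. The worked counts are CSF 60 and 1,500, blood 46,000 and 3,000,000.
- Appendix V: grades as described above. I take its named algorithm to be the ratio in Section 3.3.2.2, although the appendix does not say so. This affects 2c and 3b, not 2b.
- Section 4.2.3: clear plus two, bounded by 4 and 6.

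**Step 1. The plan's own example.** 60/1,500 = 0.04. 46,000/3,000,000 = 0.0153, and twice that is 0.0307. Since 0.04 > 0.0307, the tap is CNS disease, as Section 3.3.2.2 concludes.

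**Step 2. Blast-positive taps under both schemes**

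| CSF RBC | CSF WBC | CSF ratio | Limit (2 × blood ratio) | Section 3.3.2 | Appendix V |
|---|---|---|---|---|---|
| 50 | 2 | 0.04 | 0.0307 | CNS disease (below 100) | 2b |
| 99 | 2 | 0.0202 | 0.0307 | CNS disease (below 100) | 2b |
| 150 | 2 | 0.0133 | 0.0307 | not CNS disease | 2b |
| 1,500 | 5 | 0.0033 | 0.0307 | not CNS disease | 2c |
| 50 | 5 | 0.10 | 0.133 | CNS disease (below 100) | 2c |

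The first four rows use the blood counts of Section 3.3.2.2. The last row assumes a blood WBC of 200,000/µL at the same blood RBC: 2 × 200,000/3,000,000 = 0.133.

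**Step 3. No set of grades reproduces Section 3.3.2.** Any set that includes 2b admits the 150/2 tap, which Section 3.3.2 excludes. Any set that omits 2b drops the 50/2 tap, which Section 3.3.2 includes. Grade 2c is split in the same way.

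**Step 4. How unusual is 2c below 100 RBCs?** The lowest ratio with WBC of at least 5 and RBC below 100 is 5/99 = 0.0505. A negative algorithm then needs a blood WBC of at least 0.0505/2 × 3,000,000 ≈ 76,000/µL. At RBC 50 and WBC 5 it needs 0.10/2 × 3,000,000 = 150,000/µL. With the plan's example counts (limit 0.0307) it cannot occur. A lower blood RBC lowers these figures in proportion. The 2b discordance needs no such condition.

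**Step 5. Dose counts.** Let k be the dose at which the CSF is first clear. The text does not say whether that dose is itself one of the two additional ones.

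| k | 1 | 2 | 3 | 4 | 5 | 6 |
|---|---|---|---|---|---|---|
| Two doses after dose k: k + 2 | 3 | 4 | 5 | 6 | 7 | 8 |
| Bounded to 4–6 | 4 | 4 | 5 | 6 | 6 | 6 |
| Dose k counted as one of the two: k + 1 | 2 | 3 | 4 | 5 | 6 | 7 |
| Bounded to 4–6 | 4 | 4 | 4 | 5 | 6 | 6 |

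On the first count, one further dose fits under the maximum at k = 5 and none at k = 6. On the second, only k = 6 exceeds it.

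**The case against.** The strongest defence is that the two RBC figures do different jobs. Section 3.3.2.1 is the operative definition. Appendix V is a descriptive grading scheme, cited only for further detail. It never calls 10/µL the traumatic limit and never says that CNS 2 is not CNS disease. In 2c the word negative describes the algorithm result, so a tap can be 2c and CNS disease at once. This stands in part: Appendix V does not by itself declare any tap CNS negative. But its heading presents it as the definition, and the dosing sections do not say that CNS positive means CNS disease under Section 3.3.2.1. Because 2b and 2c fall on both sides of the Section 3.3.2 rule, the two texts cannot be treated as the same rule at different levels of detail.

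Three stronger readings are tempting and are not supported.

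- **That the plan prescribes both 1 dose and 4–6 doses for one tap.** No section says so. That contrast arises only if a site sets Section 3.3.2.1 aside and reads the relevant grade as not CNS positive.
- **That late clearance calls for 7 or 8 doses.** The explicit maximum forbids this. Nor is the dose count in general conflict with the cap: on either counting convention the total fits within the bounds for clearance by dose 4.
- **That the problem reaches every enrolled child.** All receive Induction I, but only children with blasts in the CSF and the counts above are concerned.

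**Conclusion.** The concern holds in limited form. The main-text definition and the appendix it cites classify some blast-positive taps differently, and the term that triggers extra intrathecal chemotherapy is tied to neither. A child with such a tap could be managed as CNS negative or CNS positive depending on which text the site uses. The clearest case is CNS 2b, which needs only ordinary blood counts; 2c below 100 RBCs arises only at a high blood WBC/RBC ratio. Separately, clearance first seen at dose 5 or 6 (only 6 if the dose at the first clear tap counts as one of the two) leaves the two additional doses undeliverable within the stated maximum, with no instruction for that child.

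The size cannot be given in patients, because the documents report no count of CNS-positive children. Sample size, power, significance level and the EFS test are unaffected, and risk assignment rests on marrow MRD alone (Sections 3.3.4, 3.3.5 and 4.1.3). The working assumes that the 100-RBC limit is per µL and, for 2c only, that the algorithm named in Appendix V is the ratio of Section 3.3.2.2. It should be corrected, because it governs intrathecal treatment and Section 9.2 still projects 90 further enrolments.

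**What to change.** The sponsor's clinical team should:

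1. Reconcile Sections 3.3.2.1 and 3.3.2.2 with Appendix V, including the RBC limit, its unit and the taps to which the ratio applies.
2. Tie CNS positive in Sections 4.2.1 and 4.2.3 to the reconciled definition.
3. Reconcile the two additional doses with the maximum in Section 4.2.3 for late clearance, state whether the dose at the first clear tap counts as one of the two, and align this with Section 8.1(b).

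Which limit or dose count is right is a clinical decision; none is proposed here. The cost is a protocol wording amendment, with no change to the sample size or the analysis.

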#### 3.3.2.2 Method of Evaluating Initial Traumatic Lumbar Punctures:

If the patient has leukemic cells in the peripheral blood and the lumbar puncture is traumatic and contains blasts, the following algorithm should be used to diagnose CNS disease:

$$\frac{\text{CSF WBC}}{\text{CSF RBC}} > 2X \quad \frac{\text{Blood WBC}}{\text{Blood RBC}}$$

A patient with CSF blasts, whose CSF WBC/RBC is 2X greater than the blood WBC/RBC ratio, has CNS disease at diagnosis. For example: CSF WBC = 60/ $\mu$ L; CSF RBC = 1,500/ $\mu$ L; blood WBC = 46,000/ $\mu$ L; blood RBC = 3  $\times$  10^6/ $\mu$ L:

$$\frac{60}{1,500} = 0.04 \quad > 2X \quad \frac{46,000}{3 \times 10^6} = 0.015$$

### 3.3.3 Initial CBC

The first WBC at the treating COG institution.

### 3.3.4 High Risk MDS/AML of Down syndrome

Minimal residual disease (MRD)  $\geq$  0.05% in the bone marrow at the end of Induction I.

### 3.3.5 Standard Risk MDS/AML of Down syndrome

Minimal residual disease (MRD)  $<$  0.05% in the bone marrow at the end of Induction I.

Note: For definitions of response criteria, please see [Section 10.2](#)

## 4.0 TREATMENT PLAN

Timing of protocol therapy administration, response assessment studies, and surgical interventions are based on schedules derived from the experimental design or on established standards of care. Minor unavoidable departures (up to 72 hours) from protocol directed therapy and/or disease evaluations (and up to 1 week for surgery) for valid clinical, patient and family logistical, or facility, procedure and/or anesthesia scheduling issues are acceptable (except where explicitly prohibited within the protocol).

### 4.1 Overview of Treatment Plan

See the Parenteral Chemotherapy Administration Guidelines (CAG) for children on the COG website at: [https://www.cogmembers.org/\\_files/disc/Pharmacy/ChemoAdminGuidelines.pdf](https://www.cogmembers.org/_files/disc/Pharmacy/ChemoAdminGuidelines.pdf) for special precautions and suggestions for patient monitoring during the infusion. As applicable, see the CAG for suggestions on hydration, or hydrate according to institutional guidelines.

For COG Supportive Care Guidelines see:

<https://childrensoncologygroup.org/index.php/cog-supportive-care-guidelines> under Standard Sections for Protocols.

**IMPORTANT: An aliquot of the diagnostic bone marrow sample must be sent to the laboratory of [name] at Hematologics, Inc. to facilitate later MRD measurement (for shipping information see [Section 14.2](#)). If a bone marrow sample cannot be obtained, please send a blood sample (see [Section 14.1](#)).**

#### 4.1.1 Induction I (All Patients)

All patients enrolled on AAML1531 receive Induction I as the first treatment cycle with intrathecal cytarabine, continuous infusion of cytarabine (96 hours), bolus infusion of daunorubicin and oral 6-thioguanine (6-TG) twice daily for 4 days (TAD). This cycle has a minimum duration of 28 days.

#### 4.1.2 End of Induction I Bone Marrow Aspirate (BMA)

- 1) End of Induction I BMA should be obtained between Induction Day 28 to Day 49 as guided by count recovery.
- 2) If the marrow is hypoplastic and/or there is little or no evidence of normal hematopoiesis, a repeat marrow should be performed after a further 7–21 days (based upon the peripheral blood count recovery and the clinician's judgment) and remission status assessed at this later time point. If the bone marrow remains hypoplastic, then marrow studies should be repeated every 1-3 weeks (based upon the peripheral blood count recovery and the clinician's judgment) until an accurate bone marrow status is ascertained.
- 3) Patients with an MRD value < 0.05% (MRD-negative) will be removed from study and should receive the remainder of therapy per standard of care. Patients with an MRD value  $\geq 0.05\%$  (MRD-positive) will continue treatment on the High Risk Arm (Arm B). All patients will need to wait for the MRD

assessment prior to proceeding to Induction II (partial response and refractory disease are described below).

#### 4.1.3 Risk Group Assignment

After recovery from the Induction I, patients are assigned to either the Standard or High Risk Group based on the level of MRD in the bone marrow aspirate (approximately Day 28). If there is no sign of count recovery a bone marrow aspirate should be performed no later than Day 49 from the start of Induction I to rule out the presence of refractory MDS/AML.

#### 4.1.4 Standard Risk Patients

Standard risk patients are those with an MRD level of  $< 0.05\%$  at the end of Induction I. **Arm A for Standard Risk patients closed to accrual and treatment with amendment #4A.** Patients enrolled after amendment #4A who are Standard Risk after Induction I will be removed from study and will continue treatment off protocol per standard of care. No further data will be collected on these patients.

#### 4.1.5 High Risk Patients

High risk patients are those with a MRD level of  $\geq 0.05\%$  in the bone marrow at the end of Induction I. They are treated according to Arm B. Following Induction I they receive a cycle of mitoxantrone and cytarabine (MA) as Induction II; a cycle of cytarabine and etoposide (HR-AE) as Intensification I; a cycle of Capizzi II (HD Ara-C and Asparaginase) as Intensification II for a total of 4 cycles of intensive therapy. No additional intrathecal therapy will be given after Induction I.

Patients in the High Risk Group (Arm B) will have a repeat bone marrow aspirate and MRD measurement performed at the end of Induction II (MA) as part of standard clinical care for patients with previously positive MRD. The MRD result at the end of Induction II will be reported. However, MRD data obtained at the end of Induction II will not be used for treatment decisions but will aid in evaluating the performance of the MRD test. HR patients in a morphologic remission but MRD-positive should remain on protocol therapy.

#### 4.1.6 Peripheral Blood Count Recovery

- 1) If the bone marrow after Induction I shows a complete response (CR, see [Section 10.2](#)), Induction II will be administered when the ANC  $\geq 1000/\mu\text{L}$  and platelets  $\geq 100,000/\mu\text{L}$ . A CBC should be repeated every 4 days until counts are adequate.
- 2) For all cycles, if the counts have not recovered by Day 49, repeat the bone marrow studies. A bone marrow biopsy is encouraged.
- 3) If the platelet count is rising progressively to  $75,000/\mu\text{L}$  but has not reached  $100,000/\mu\text{L}$  by three weeks after the ANC has reached  $1,000/\mu\text{L}$ , patients may proceed to the next cycle of therapy.
- 4) Note: Patients with a Partial Response (PR) or Refractory Disease (RD) ( $> 5\%$  leukemic blasts confirmed by MRD) should start Induction II (MA) on the High risk Arm (Arm B) regardless of blood counts. Patients who have a

positive MRD ( $\geq 0.05\%$  leukemic blasts) at the end of Induction I should start Induction II (MA) on the High risk Arm (Arm B) no later than Day 56 even if they have not met criteria for count recovery.

#### 4.1.7 Use of Cardioprotectant (Dexrazoxane)

The use of dexrazoxane in association with anthracyclines will be left to institutional preference and per institutional guidelines. Therefore, is neither mandated nor prohibited by the AAML1531 protocol. Data on dexrazoxane use and cardiac outcomes (shortening fraction and ejection fraction) will be prospectively collected during chemotherapy and follow-up.

**NOTE:** As per the product monograph ZINECARD® (dexrazoxane) is indicated for reducing (preventing) the incidence and severity of cardiotoxicity associated with doxorubicin administration for the treatment of metastatic breast cancer in patients who have already experienced a partial response or at least maintained stable disease. This is based on efficacy for cardioprotection in metastatic breast cancer patients who had already received at least 300 mg/m^2 of doxorubicin.

## 4.2 Induction I (All Patients)

4.2.1 Therapy Delivery Map – Induction I (All Patients) Induction I is a minimum of 28 days.			Patient COG ID		DOB			
Criteria to start Induction I are the patient eligibility criteria described in Section 3.2 . This Therapy Delivery Map is on 2 pages.								
DRUG	ROUTE	DOSAGE		DAYS	IMPORTANT NOTES			
Intrathecal Cytarabine (IT ARAC)	IT	Age (months)	Dose	1*	*If not given at time of diagnostic LP (see Section 4.2.3 ). CNS positive patients receive additional doses of IT ARAC as detailed in Section 4.2.3 .			
Cytarabine (ARAC IV)	Continuous IV infusion for 96 hrs	Age (months)	Dose	1-4				
DAUNOrubicin (DAUN)	Slow IV push or infusion over 1-15 minutes	Age (months)	Dose	1-4	See Section 4.2.3 for additional administration guidelines. Dexrazoxane may be administered at the discretion of the treating team. Please record below. See Section 4.1.7 .			
Thioguanine (TG)	PO	Age (months)	Dose	1-4	Administer dose in AM & at bedtime. Round doses to nearest 10 mg if using the tablet formulation.			
Ht cm	Wt kg	BSA m 						
Date Due	Date Given	Day	IT ARAC mg	ARAC IV mg	DAUN mg	TG mg	Studies	Dexrazoxane Yes/No
Enter calculated dose above and actual dose administered below								
		1	_____ mg*	_____ mg	_____ mg	_____ mg	_____ mg	a – 1 #
		2		_____ mg	_____ mg	_____ mg	_____ mg	
		3		_____ mg	_____ mg	_____ mg	_____ mg	
		4		_____ mg	_____ mg	_____ mg	_____ mg	a
		5						
		6						
		7						
		8						a, b, c, d
		9						
		10						
		11						a
		12						
		13						
		14						
		15						a, b, c, d
		16						
		17						
		18						a
		19						
		20						
		21						
		22						a, b, c, d
		23						
		24						
		25						a
		26						
		27						
		28	Standard risk patients (MRD < 0.05%) will be removed from study and High risk patients (MRD ≥ 0.05%) continue with Induction II of Arm B (see Sect 4.3 ) when ANC ≥ 1000/µL and a platelet count ≥ 100, 000/µL. NOTE: exceptions exist, as detailed in Section 4.16 .				a, k, l, m	

See [Section 5.0](#) for Dose Modifications for Toxicities and the COG Member website for Supportive Care Guidelines.

\* PRIOR TO THERAPY

4.2.2 Required Observations in Induction I

**All baseline studies (a-m below) must be performed prior to starting protocol therapy unless otherwise indicated below.**

- a. Physical exam, CBC with differential & platelets, twice weekly while in the hospital.
- b. Creatinine, BUN, weekly while in the hospital.
- c. Electrolytes (Ca++, Mg++, PO4), weekly while in the hospital.
- d. AST, ALT, bilirubin (unconjugated and conjugated), weekly while in the hospital.
- e. Height, weight.
- f. ECG.
- g. ECHO or MUGA.
- h. Unilateral bone marrow aspirate (BMA); biopsy if unable to obtain a BMA
- i. Bone marrow baseline immunophenotype (Immunophenotyping including CD41 and/or CD61, CD33, CD34, CD14, CD7 and Gly-A is strongly recommended).
- j. CSF cell count and cytospin.
- k. BMA for MRD, submit sample to Hematology (peripheral blood may be used for baseline sample, see [Section 14.1](#)).
- l. Optional bone marrow sample for *GATA1* mutation analysis (see [Section 14.1](#)).
- m. Optional bone marrow sample for banking (see [Section 14.1](#)).

**OBTAIN OTHER STUDIES AS REQUIRED FOR GOOD CLINICAL CARE.**

**COMMENTS**

#### 4.2.3 Induction I Treatment Details (All Patients)

Criteria to start Induction I are the patient eligibility criteria described in [Section 3.2](#).

##### **Intrathecal Cytarabine:**

The dose of intrathecal (IT) cytarabine may be given at the time of the diagnostic lumbar puncture. If IT cytarabine is not given at time of diagnostic LP, then administer on Day 1 of Induction I. If IT cytarabine is given prior to diagnosis, a separate institutional consent must be obtained.

Age-based dosing:

Age (months):	Dose:
0 to < 13 months	20 mg
13 to < 25 months	30 mg
25 to < 36 months	50 mg
≥ 36 to < 48 months	70 mg

**For CNS positive patients:** IT cytarabine will be given twice weekly until the CSF is clear plus two additional intrathecal treatments (for a minimum of 4 and maximum of 6 doses). Patients with persistent CNS leukemia after 6 doses of IT cytarabine will be taken off protocol therapy.

